7.5 Medical History and Concurrent Medical Conditions

Medical history is defined as significant conditions or diseases that resolved at or prior to the time of informed consent. Concurrent medical conditions are defined as significant conditions or diseases that are present or ongoing at signing of informed consent.

Medical history and concurrent medical conditions will be coded by system organ class and preferred term using the Medical Dictionary for Regulatory Activities (MedDRA, version 20.0 or higher). No summary statistics for medical history and concurrent medical conditions will be provided.

Medical history and concurrent medical conditions will be listed by site and subject number. The listing will contain subject identifier, hepatic function group, system organ class (SOC), preferred term (PT), whether there was any medical history or concurrent condition, and, if yes, a detail of the medical history or concurrent condition.

There will be no inferential analysis of medical history and concurrent medical conditions.

7.6 Medication History and Concomitant Medications

Medication history information includes any medication relevant to eligibility criteria stopped at or within 30 days prior to signing of informed consent. Concomitant medications are recorded on the eCRF and include any medications, other than study drug, taken at any time from signing of informed consent through the end of the study. No summary statistics for medication history and concomitant medications will be provided.

All medication history and concomitant medications will be listed by site and subject number. The listings will contain subject identifier, hepatic function group, World Health Organization Drug Dictionary (WHODrug) preferred medication name, dose, unit, frequency, route, start date, stop date, whether the medication was ongoing, and reason for use. No inferential statistics will be presented.

Medication history and concomitant medications will be coded using the WHODrug 2018 March DDE B2 or higher.

7.7 Study Drug Exposure and Compliance

The date, start and end of infusion time of study drug administration in each group for each subject will be reported in the data listings. Summaries of TAK-954 PK data will be provided for each group, details can be found in section 7.9. No other summary statistics for the extent of exposure to study drug or compliance calculations will be performed.

7.8 Efficacy Analysis

Not applicable.

7.9 Pharmacokinetic Analysis

All PK summaries and analyses will be based on the PK set.

PK blood for plasma concentration and urine samples for TAK-954 (and metabolites, if possible), and plasma protein binding will be collected as specified in the Schedule of Trial Procedures (See [Appendix C](#)).

All efforts will be made to obtain the PK samples at the exact nominal time relative to dosing. However, samples obtained within 10% of the nominal time from dosing will not be captured as a protocol deviation, as long as the exact time of dosing and the sample collection is noted on eCRF.

7.9.1 Summary of Concentrations in Plasma

Descriptive statistics (e.g. mean, standard deviation, standard error, %CV, minimum, median and maximum) will be used to summarize concentrations of TAK-954 (and metabolites, if possible) according to the hepatic function group (healthy subjects and mild, moderate, severe hepatic impairment). If applicable, the amount of TAK-954 excreted in urine will also be summarized by hepatic function group using descriptive statistics. For protein binding data, concentration, unbound percentage, bound percentage and recovery percentage will be summarized according to hepatic function group using descriptive statistics.

Linear and semi-logarithmic plots of the mean and individual concentration-time curves will be provided.

Individual concentration data will be presented in the data listing.

7.9.2 Analysis of Pharmacokinetic Parameters

PK parameters will be compared between normal and hepatically-impaired groups, classified by Child-Pugh Score and summarized descriptively. PK parameters of TAK-954 will be derived using noncompartmental analysis methods and will be determined from the concentration-time data for all evaluable subjects. Actual sampling times, rather than scheduled sampling times, will be used in all PK computations involving sampling times.

The following plasma PK parameters (free and total) for TAK 954 will be calculated:

- C_{\max}
- AUC_{∞}
- AUC_{last}

Specific or additional PK parameters may be added as appropriate per the Clinical Pharmacology Analysis Plan (CPAP).

Descriptive statistics (e.g. mean, standard deviation, standard error, %CV, minimum, median and maximum) will be used to summarize PK parameters (expressed as free and total) according to the hepatic function group (healthy subjects and mild, moderate, severe hepatic impairment). In addition, geometric means will be calculated for C_{max} and AUCs.

All pharmacokinetic parameters will be provided in a data listing.

An analysis of variance (ANOVA) will be performed on log transformed C_{max} , AUCs (total and free) and CL to compare each hepatically-impaired group with the normal hepatic function group and 90% confidence intervals for the ratio of central values from each hepatic impairment group versus normal function group will be provided. In addition, an analysis of covariance (ANCOVA) with hepatic function group as a fixed effect, age, gender and body weight as covariates will be performed on log transformed C_{max} , AUCs (total and free) and CL to investigate effect of covariates on the relationship between TAK-954 PK parameters and level of hepatic impairment. Tests will be performed on all covariates, 0.05 significance level will be used.

In addition, the relationship between Child-Pugh scores, baseline serum bilirubin, serum albumin, prothrombin time and TAK-954 C_{max} , C_{maxu} , AUC_{last} , AUC_{lastu} , AUC_{∞} and $AUC_{\infty u}$ will be evaluated graphically. Regression approaches will be used to evaluate these relationships if appropriate.

Additional analyses will be included, if appropriate. Any deviation from the analysis plan will be reported in the Clinical Study Report.

Individual pharmacokinetic parameter data will be presented in the data listing.

7.10 Other Outcomes

Subject must sign a PGx informed consent/be consented for sampling of whole blood for PGx analysis to occur. PGx sampling is optional.

Whole blood samples for DNA and RNA isolation will be collected from each consented subject in the trial. If necessary and feasible, a second aliquot of blood may be taken at a later time point if isolation of DNA from the first sample was not successful or possible.

The sample collection information for PGx will be listed.

7.11 Safety Analysis

Safety analyses include AEs, clinical laboratory evaluations, vital sign results, 12-lead ECG results, and other safety parameters. The safety set will be used for all summaries of safety parameters.

7.11.1 Adverse Events

A pretreatment event (PTE) is defined as any untoward medical occurrence in a clinical investigation subject who has signed informed consent to participate in a study, but prior to administration of any study drug; it does not necessarily have to have a causal relationship with

study participation. A treatment-emergent adverse event (TEAE) is defined as any sign, symptom, syndrome, or new illness, regardless the relationship to study drug, which occurs on or after the administration of the study drug and no more than 30 days after receiving the study drug (onset date minus date of dose +1 \leq 30). A TEAE may also be a pretreatment AE or a concurrent medical condition diagnosed prior to the date of study drug that increases in severity after the start of dosing. Any event with partially or completely missing onset date information will be considered treatment emergent unless the available information indicates that the onset occurred outside the window (onset date - date of dose +1 \leq 30).

All AEs will be coded by system organ class (SOC) and preferred term (PT) using the Medical Dictionary for Regulatory Activities (MedDRA, version 20.0 or higher).

AEs are recorded in the eCRF as being related or not related to study drug and study procedure. AEs that are recorded as related to study drug and/or study procedure will be summarized separately. AEs will also be presented by intensity/severity (mild, moderate, and severe).

When calculating the frequency and percentage of subjects who reported AEs, a subject will be counted only once for each SOC or PT when multiple AEs are coded to the same SOC or PT. For the intensity or relatedness summaries, if a subject reports multiple AEs coded to the same SOC or PT, the AE with maximum intensity or strongest relationship will be included in the summary.

AEs with missing intensity will be listed as such in the AE listings, however, will be summarized as severe in summary tables. If the relationship of an event is missing, the relationship for the event will be considered to have been related.

The TEAE summary tables will include numbers and percentages of subjects experiencing at least one TEAE by SOC and PT and will be tabulated by hepatic function groups and overall. The following is a list of TEAE summary tables to be generated:

- Overview of TEAEs.
- TEAEs by SOC and PT
- Subject Mappings for TEAEs.
- TEAEs by PT.
- Serious TEAEs by SOC and PT
- Most Frequent Non-Serious TEAEs by PT ($\geq 5\%$ subjects in any group)
- Drug-Related TEAEs by SOC and PT.
- Relationship of TEAEs to Study Drug by SOC and PT (related vs not related).
- Intensity of TEAEs by SOC and PT.
- Intensity of Drug-Related TEAEs by SOC and PT.
- PTE by SOC and PT.

Data listings will be provided for all AEs including TEAEs, AEs leading to trial drug discontinuation, and SAEs.

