7.1.3 Conventions for Missing Adverse Event Dates

There will be no imputation of incomplete or missing adverse event dates.

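### In SAP 7.11.1 the formula in the missing-onset-date rule omits the lower limit that the TEAE definition in the same paragraph states in words

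*SAP*

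**What the plan says.** SAP 7.11.1 sets a default and an exception to it. The default reads: "Any event with partially or completely missing onset date information will be considered treatment emergent". The exception, later in the same sentence, carries the formula at issue: "unless the available information indicates that the onset occurred outside the window (onset date - date of dose +1 \leq 30".

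The same paragraph also contains:

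- **The TEAE definition**, with two limits in words: an event "which occurs on or after the administration of the study drug and no more than 30 days after receiving the study drug". The same one-sided formula follows it in brackets.
- **The PTE definition:** an event after consent "but prior to administration of any study drug".
- **A route from predose to TEAE:** an earlier event or condition qualifies only if it is one "that increases in severity after the start of dosing".

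The table list at the end of the section includes a separate summary, "PTE by SOC and PT". SAP 7.1.3 states: "There will be no imputation of incomplete or missing adverse event dates".

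Protocol 10.2.9.1 starts adverse event collection at informed consent and ends routine collection at the Follow-up Visit, 10 to 14 days after the dose. Protocol 11.1.4.1 carries the same upper-limit formula. Neither document says which items count as available information for the exception, for example whether a stop date may be used.

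**The concern.** Words and formula disagree within a rule that classifies events, and the formula is the part most easily turned into code. Coded as printed, the exception tests only whether onset was too late. An event whose partial onset date, or whose stop date, places it before the infusion would pass the test and enter the TEAE tables, although the paragraph elsewhere calls it a PTE. Depending on how the PTE table is programmed, it would then appear in both tables or only in the wrong one.

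Safety and tolerability is the secondary objective, and TEAEs are tabulated by hepatic function group. SAP 7.11.1 also summarizes missing intensity as severe and treats a missing relationship as related. A poorly documented predose event could therefore reach the severe and drug-related tables too. The pharmacokinetic analysis is not touched.

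**Working it through.** Let d = onset date − date of dose.

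**Inputs**

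- Printed rule (SAP 7.11.1): inside the window if d + 1 ≤ 30.
- Worded rule (TEAE definition, same section): inside if d ≥ 0 and d + 1 ≤ 30.
- Earliest onset considered: d = −28, the first day of the screening column in the Schedule of Trial Procedures. This assumes consent no earlier than Day −28; an earlier consent only adds predose days.
- Latest routinely collected onset: d = +14 (Protocol 10.2.9.1).

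**Step 1. Evaluate both rules.**

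| d | d + 1 | Printed rule | Worded rule |
|---|---|---|---|
| −28 | −27 | inside | outside |
| −10 | −9 | inside | outside |
| −1 | 0 | inside | outside |
| 0 | 1 | inside | inside |
| +14 | 15 | inside | inside |
| +29 | 30 | inside | inside |
| +30 | 31 | outside | outside |

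**Step 2. Count days over the collection span.** From d = −28 to d = +14 there are 28 + 1 + 14 = 43 calendar days. The printed rule keeps all 43 inside. The worded rule keeps 15 (d = 0 to +14) and puts the 28 predose days outside. These are calendar days that pass an inequality, not events at risk.

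**Step 3. Which limit does any work.** The printed rule first excludes an event at d = +30, and the largest value in routine collection is 15. Only an onset learned of later, such as a related SAE reported after the collection period (Protocol 10.2.9.3), could fail it. For routinely collected events, the exception as printed is empty.

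**Step 4. Hypothetical cases.** Take consent on 20 March and dosing on 10 April.

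- Onset recorded as March, day missing: possible onsets 20 to 31 March, d = −21 to −10, values −20 to −9. All are ≤ 30, so TEAE as printed, although onset is certainly predose.
- Onset missing, stop date 7 April: possible onsets 20 March to 7 April, d = −21 to −3, values −20 to −2. TEAE as printed, although the event ended before dosing.
- The first onset date that the formula excludes is 10 May (d = +30).

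**Step 5. Day 1.** At d = 0 the date cannot separate an onset before the infusion from one after it, so a lower limit on dates alone is not enough. Protocol 10.2.9.2 has start and stop times recorded, and SAP 7.7 has infusion start times listed, so the comparison is possible.

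**Step 6. Size of one error.** One subject in a group of 8 is 1/8 = 12.5 percentage points. Protocol 6.3 allows fewer than 8 in the severe group; with 6 it would be 1/6 = 16.7 points and with 4 it would be 1/4 = 25 points (illustrative sizes).

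**The case against.** The strongest reply is that the exception speaks of the window, and the only window the SAP defines is the two-sided one in the TEAE definition. The one-sided formula follows those two-sided words as well, so it is best read as shorthand for the 30-day limit. If the formula overrode the words, every fully dated predose event would also be a TEAE and the PTE table would have no purpose. This stands as to intent.

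A reader might therefore go too far in three ways:

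- **That the SAP prescribes counting predose events as TEAEs, and that predose information can never remove one.** The text does not support this. Available information is unrestricted, and a partial onset date or a predose stop date can fall under it.
- **That this sentence alone decides the class because imputation is barred.** It does not. The PTE and TEAE definitions in the same paragraph also bear on the class, and 7.1.3 only bars filling in dates.
- **That the impaired groups' TEAE rates would be inflated against the healthy group.** This is conjecture. Protocol 10.1 keeps conditions present at consent, and intermittent events of underlying disease, out of the adverse event record unless they worsen, which removes much of the background symptom load in cirrhosis.

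Exposure is also limited. Start and stop dates and times are required for each event, Protocol 16.1 provides logic checks and queries for missing or inconsistent dates, and Protocol 11.1 adds a data review before lock. All adverse events are listed, so a misclassified event would remain visible.

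None of this makes the printed formula agree with the definition it is meant to express.

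**Conclusion.** The formula in the missing-date rule is wrong as written against the SAP's own TEAE and PTE definitions. It is a drafting error with a programming risk; the probable intent is two-sided. Harm requires a predose event whose onset date is still incomplete after data cleaning, together with code that follows the formula and not the words. The number of such events cannot be known from the documents and is probably very small. One event could still visibly move a percentage in groups this small. The effect is confined to a descriptive, secondary safety summary.

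**What to change.** In SAP 7.11.1, replace the bracketed expression with both limits and name the information that may be used:

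- An event with an incomplete onset date is treatment-emergent unless a partial onset date or time, or a stop date or time before dosing, shows onset before the start of infusion or after the stated upper limit.
- In dates, the window is 1 ≤ onset date − date of dose + 1 ≤ upper limit, with onset time deciding events on Day 1.
- Events shown to be predose go to the PTE table unless they increase in severity after dosing.
- State the upper limit once. The formula stops at dose date + 29, while the wording can be read as dose date + 30. With follow-up at 10 to 14 days this has no practical effect.

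Use the same expression wherever the formula is repeated. The cost is one clause and one line of code. Events whose timing is truly unknown still default to TEAE, so the conservative handling is kept.

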7.11.2 Clinical Laboratory Evaluations

Clinical laboratory tests consist of chemistry, hematology, urinalysis, and other tests. Clinical laboratory tests will be assessed using the Safety Set and will be evaluated and presented using International System of Units (SI) units unless otherwise stated. Refer to [Appendix C](#) for scheduled clinical laboratory test measurements.

Clinical laboratory variables will be summarized by hepatic function group with descriptive statistics (N, mean, median, SD, minimum and maximum) for Baseline, postdose, and change from Baseline to postdose values. Instead of Calcium, corrected Calcium will be summarized. Corrected Calcium can be calculated via the following formulas.

- In conventional units: $\text{Corrected Calcium [mg/dL]} = (0.8 * (4[\text{mg/dL}] - \text{Albumin}[\text{mg/dL}])) + \text{Calcium}[\text{mg/dL}]$.
- In SI units: $\text{Corrected Calcium [mmol/L]} = (0.02 * (40[\text{g/L}] - \text{Albumin}[\text{g/L}])) + \text{Calcium}[\text{mmol/L}]$.

Here 4mg/L and 40g/L represent normal Albumin levels.

Only the scheduled measurements will be included in the summary. The baseline value will be defined as the pretreatment assessment immediately prior to administration of study drug. No inferential statistics will be presented.

All clinical laboratory data in SI and conventional Units will be presented in the data listings.

7.11.3 Vital Signs

Descriptive statistics (N, mean, SD, median, minimum, and maximum) will be used to summarize vital sign parameters at baseline, each post-baseline visit, and change from baseline to each post-baseline visit. No inferential statistics will be presented.

For each vital sign parameter, boxplots for predose/ postdose values and the change from the predose by hepatic function group will be prepared.

Individual results of vital signs that meet Takeda's markedly abnormal criteria (see [Appendix A](#)) will be summarized and provided in the data listings. If a subject has a MAV for a particular vital sign parameter, all visits for that subject for that parameter will be listed. The number and percentage of subjects with at least 1 postdose MAV signs measurement will be summarized by hepatic function group. The mapping of the subjects who meet the MAV criteria will be listed as a table. All observations, including ones at unscheduled visits, will be included in the MAV evaluation and summaries.

All vital sign results for all subjects in the Safety Set will be listed by subject in the data listings and markedly abnormal values will be flagged.

7.11.4 12-Lead ECGs

The scheduled 12-lead ECG data will be collected according to [Appendix C](#). The ECG parameters include heart rate, PR-interval, QRS-duration, QT-interval, QTcF interval, and the interpretation of the ECG profile by the principal investigator.

Descriptive statistics (N, mean, SD, median, minimum, and maximum) of ECG parameters will be presented for baseline, each post-baseline visit, and changes from Baseline in quantitative ECG parameters to each post-baseline visit. Only the scheduled measurements will be included in the summary. If more than 1 ECG parameter is measured at the same scheduled time point, the latest value will be used. No inferential statistics will be presented.

Individual results of quantitative ECG parameters from the 12-lead safety ECGs that meet Takeda's markedly abnormal criteria (see [Appendix B](#)) will be provided in the data listings. Shift tables will be generated to show the investigator's ECG interpretations at each postdose collection by the interpretation at Baseline.

All ECG data will be presented in the listings. ECG MAVs will be flagged in the listings.

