9.0 TRIAL PROCEDURES

The following sections describe the trial procedures and data to be collected as indicated in the Schedule of Trial Procedures (Section 3.0). For each procedure, subjects are to be assessed by the same investigator or site personnel whenever possible. Please note that it may become necessary to perform the following procedures at unscheduled time periods, per the discretion of the investigator. For information regarding procedures that are scheduled concurrently, see Section 6.3.1.

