9.1.9 BMI

BMI equals a person's weight in kilograms divided by height in meters squared ($BMI = \text{kg}/\text{m}^2$).

BMI will be rounded to the nearest whole number according to the standard convention of 0.1 to 0.4 round down and 0.5 to 0.9 round up.

9.1.10 12-Lead ECG

Special care must be taken for proper lead placement by qualified personnel. Skin should be clean and dry before lead placement. Subjects may need to be shaved to ensure proper lead placement. Female subjects may need to remove their bras.

Subjects should be resting in a semirecumbent position for at least 5 minutes before each ECG measurement.

QT intervals with Fridericia correction method (QTcF) will be used to calculate QT intervals in this trial.

A predose ECG will be obtained within approximately 30 minutes before dosing. This measurement will be used as the baseline. The principal investigator should arrange to have a trial cardiologist available as needed to review ECG tracings with abnormalities.

If a subject demonstrates an increase in QTcF interval ≥ 40 msec compared with a predose baseline measurement, the ECG will be repeated within 5 minutes. The average value of the QTcF interval from the 2 ECGs will represent the value at that time point. If the average QTcF interval increase from Baseline for any postdose time point is ≥ 40 msec, the subject will continue to be monitored by repeat 12-lead ECGs every 60 minutes for at least 4 hours or until the QTcF is within 40 msec of the baseline value. If prolongation of the QTcF interval ≥ 40 msec persists, a consultation with a trial cardiologist may be appropriate and the sponsor should be notified.

If the QTcF interval is ≥ 500 msec, the sponsor should be notified and the ECGs should be reviewed by a cardiologist. The subject should be telemetry-monitored (until the QTcF is <500 msec) or should be considered for transfer to a location where closer monitoring is available.

If the subject has unstable hemodynamics, or has any clinically significant dysrhythmias noted on telemetry, the subject should be immediately transferred to an acute care setting for definitive therapy.

If repeat ECGs are required, the clinical site will decide whether to leave the electrodes in place or mark the position of the electrodes for subsequent ECGs. To mark the position of the electrodes, 12-lead electrode sites will be marked on the skin of each subject with an ECG skin marker pen to ensure reproducible electrode placement.

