7.13 Changes in the Statistical Analysis Plan

**8.0 BASED ON CONSULTATION WITH PHARMACOVIGILANCE, THE
CORRECTED CALCIUM WILL BE SUMMARIZED, RATHER THAN
CALCIUM AS STATED IN THE PROTOCOL. REFERENCES**

1. A Phase 1, Nonrandomized, Open-Label Trial to Evaluate the Effect of Hepatic Impairment on the Single Dose Pharmacokinetics of Intravenous TAK-954, Takeda Development Center Americas, Inc. and Takeda Development Centre Europe Ltd., Amendment 01, Trial No. TAK-954-1006, dated 06 October, 2017.

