Appendix B Criteria for Identification of Markedly Abnormal 12-Lead ECG Parameters

Parameter	Unit	Lower Criteria	Upper Criteria
HR	bpm	<50	>120
QTcF-interval	msec	≤50	≥500 OR ≥30 change from baseline and ≥450

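### After a triggered repeat ECG the protocol's QTcF value is the average of two readings, but the SAP tabulates the latest one, or the first if the repeat is coded unscheduled

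*SAP*

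**What the plan says.** Protocol 9.1.10 (12-Lead ECG) takes the predose ECG as baseline. If a later QTcF is at least 40 msec above it, "the ECG will be repeated within 5 minutes", and then: "The average value of the QTcF interval from the 2 ECGs will represent the value at that time point". The same section uses that averaged increase to decide whether hourly repeat ECGs follow.

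SAP 7.11.4 (12-Lead ECGs) covers descriptive statistics for each visit and for change from baseline. Two rules select the data. First, "Only the scheduled measurements will be included in the summary". Second, "If more than 1 ECG parameter is measured at the same scheduled time point, the latest value will be used". It also states that "All ECG data will be presented in the listings". It contains no averaging rule and does not say whether a repeat under protocol 9.1.10 counts as scheduled. Protocol 9.0 accepts that "it may become necessary to perform the following procedures at unscheduled time periods", so an unscheduled category of procedures exists.

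The only change stated at SAP 7.13 concerns laboratory data: "CORRECTED CALCIUM WILL BE SUMMARIZED, RATHER THAN" uncorrected calcium.

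In SAP Appendix B, the lower criterion for a markedly abnormal QTcF reads "QTcF-interval msec ≤50".

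**The concern.** The protocol defines a QTcF value for exactly those time points where a large increase has been seen, and the SAP tabulates a different number there. The discrepancy is not random. The repeat is taken only because the first reading was high, so the second tends to fall back toward the subject's true level. Taking the latest reading tends to pull the reported change down. Dropping an unscheduled repeat and keeping the first tends to push it up. The direction therefore depends on a coding choice that the SAP leaves open.

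What is at stake is the mean, SD, maximum and change from baseline of QTcF at triggered time points. With about 8 subjects per group, one subject can set the reported maximum. The tables could also disagree with conduct: a subject monitored further because the average reached 40 msec could appear in the summary with a change below 40.

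**Working it through.** The documents give no figure to reproduce, so the check sets the rules side by side and then sizes the gap.

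**Rules applied to two readings, f (first) and r (repeat)**

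- Protocol 9.1.10: (f + r)/2
- SAP 7.11.4, repeat counted as scheduled: r
- SAP 7.11.4, repeat coded unscheduled: f

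The error against the protocol value is −(f − r)/2 in the first SAP case and +(f − r)/2 in the second.

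**Worked examples (assumed readings; changes from baseline in msec)**

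| First | Repeat | Protocol average | SAP, repeat scheduled | SAP, repeat unscheduled |
|---|---|---|---|---|
| +50 | +36 | +43 | +36 (error −7) | +50 (error +7) |
| +45 | +27 | +36 | +27 (error −9) | +45 (error +9) |

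In the first row the average reaches the protocol's 40 msec criterion for continued monitoring, but the table could show 36. In the second it does not, but the table could show 45. For the first row, one such subject in a group of 8 moves the group mean by 7/8 = 0.875 msec in either direction.

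**Expected error per subject and time point**

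Assumptions, none of them from the documents: both readings of the change are independent and normal around the true change, with SD 8 to 12 msec, and a repeat is taken when the first is at least 40. Then

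E(average − latest) = E(first − average) = SD × φ((40 − true change)/SD) / 2,

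with φ the standard normal density and untriggered time points contributing zero. For a true change of 35 and SD 8, this is 8 × φ(0.625)/2 = 1.31; with SD 12 it is 12 × φ(0.417)/2 = 2.19. Simulation with 2,000,000 pairs per setting agrees.

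| True change (msec) | Expected error, SD 8 to SD 12 (msec) |
|---|---|
| 10 | 0.001 to 0.11 |
| 20 | 0.07 to 0.60 |
| 30 | 0.7 to 1.7 |
| 35 | 1.3 to 2.2 |
| 40 | 1.6 to 2.4 |

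The chance of a trigger is 0.01% to 0.6% at a true change of 10 and 27% to 34% at 35.

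**Error where a repeat is actually triggered**

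A second simulation also gave the predose baseline a measurement error (SD 5 to 15 msec per reading, true change 10 to 30; the cell with SD 5 and change 10 had too few triggers to use). Among triggered time points, the latest reading lay about 3 to 10 msec below the average, and the first reading lay the same amount above it.

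**Appendix B lower limit**

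Under Fridericia's correction, raw QT = QTcF × (60/HR)^(1/3). Within Appendix B's own heart-rate limits, a QTcF of 50 msec needs a raw QT of 50 × (60/50)^(1/3) = 53.1 msec at 50 bpm, or 50 × (60/120)^(1/3) = 39.7 msec at 120 bpm. No plausible ECG gives such values.

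**The case against.** The strongest reply is that this hardly matters. SAP Appendix C schedules about 7 postdose ECGs per subject (1, 2 and 4 hours, Days 2, 3 and 4, and follow-up), so 32 subjects give 7 × 32 = 224. At the trigger rates above for a true change of 10 msec, about 0.02 to 1.4 repeats would be expected in the whole trial. Two readings minutes apart are also probably correlated; for a given SD, a correlation ρ multiplies the expected error by (1 − ρ). Both points stand as limits on size. The trigger count is, however, sensitive to its assumptions: with baseline error included, the simulated rate at a true change of 10 is 0.4% for SD 8 and 1.7% for SD 10, or roughly 1 to 4 repeats in 224.

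Second, a mandated repeat tied to its time point most naturally counts as scheduled, so the first-reading case may not arise. That is a fair reading, but the SAP does not state it, and the natural reading still gives the latest value rather than the average.

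Third, the averaging rule sits among the procedures, and protocol 11.1 leaves analysis variables to the SAP. Yet 9.1.10 says what represents the time point, and protocol 11.1.4.4 sets no other rule. An average might be derived upstream under the Data Management Plan, but neither document says so.

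Fourth, averaging QTcF alone means it will not match the QT and heart rate tabulated for that time point. This is true, but it follows from the protocol's own rule, which covers QTcF only, and a table footnote deals with it.

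**Conclusion.** The concern holds. Followed as written, SAP 7.11.4 produces a QTcF summary value that the protocol does not define, without declaring the departure. The error is half the difference between the two readings. It is systematic in direction once the coding is fixed, but that coding is unstated. The expected size ranges from negligible at small true changes to about 2 msec per subject and time point near the trigger, under the assumed SDs and independence.

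The scope is limited to descriptive QTcF summaries. Both readings remain in the listings, abnormal-value flags apply to individual results, monitoring during the study follows the protocol, and the PK endpoints are untouched. This is a correction that should be made, not a threat to the trial's conclusions. The Appendix B limit is a separate, secondary item: it is ineffective as printed, and the documents do not show what was intended.

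**What to change.** In SAP 7.11.4, state that for a repeat triggered under protocol 9.1.10 the QTcF time-point value, and its change from baseline, is the average of the two ECGs, whether or not the repeat is coded as scheduled. Keep the latest-value rule for other duplicates, and footnote the tables to say that only QTcF is averaged. If the sponsor prefers its present rule, it should say how triggered repeats are coded and declare and justify the departure under 7.13.

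Check the lower QTcF limit in Appendix B against the sponsor's source criteria and correct it if it was mis-transcribed.

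The cost is a sentence or two of SAP text, a few lines of programming and one table check. No new data are needed.
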